On Day 1 of the naltrexone induction, participants are pre-treated with prochlorperazine, clonidine, and clonazepam, followed by the first dose of naltrexone 1.5mg. If the first dose of naltrexone is tolerated, a second dose of 1.5mg will be administered. Ascending split doses of naltrexone will be titrated up slowly, until the final total dose of 15mg has been given on Day 3 (Day 1: 1.5-3mg, Day 2 : 3-6mg, Day 3: 15mg). Ancillary medications will be offered daily during the induction week and will include clonidine for myalgias, prochlorperazine for nausea, clonazepam to reduce anxiety and dysphoria, and trazodone or zolpidem for insomnia. Participants will be provided take-home doses of ancillary medications in small doses for one week post-administration of Vivitrol. Once a total of 15mg of naltrexone has been tolerated (at least 1.5 hr. observation), the participant may receive 380mg IM Vivitrol. As noted in the section for Procedures for Missed Doses of Vivitrol, if relapse is suspected (the participant reports opioid use, and/or has a positive UDS for opioids) and there is a risk that the participant has developed physical dependence (e.g., delay in receiving scheduled injection or subjective effects suggesting that the block is incomplete) a naloxone challenge will be administered before the participant receives their next injection.

For female participants, a urine pregnancy test will be obtained on the day of Vivitrol administration. If at any time during the study a female participant has a positive urine pregnancy test, this will be reported to the FDA and IRB, the participant will be discontinued from the study, and transitioned to a treatment program in the community.

If a participant is unable to receive Vivitrol on induction Day 3, because they were unable to receive naltrexone due to opioid intoxication or severe withdrawal, the participant will be given up to two additional days to attempt the oral naltrexone titration and Vivitrol induction. **If a patient fails to succeed with the naltrexone initiation procedure, the study team will provide the patient with a weekly supply of buprenorphine, and will be provided with a referral.**

Vivitrol Injections: Vivitrol will be administered as an intramuscular injection (380mg) in one buttock by one of the research psychiatrists or research nurse, who are currently trained and administer Vivitrol in other

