protocols. Participants will be offered a second injection 4 weeks post administration of the first injection, and a 3rd injection 4 weeks later.

Procedures for Missed Doses of Vivitrol: If a patient misses a scheduled second or third injection and takes an opioid during at least two of the seven days following the date of the scheduled injection, relapse will be suspected (the participant reports recent opioid use, and/or has a positive UDS for opioids), a naloxone challenge may be performed, if appropriate, using 0.8mg naloxone IM. The patient is followed clinically and withdrawal symptoms are assessed over the next hour. If the challenge is negative, the administration of Vivitrol will be resumed. However, because there are blood levels and partial blockade beyond four weeks after the initial administration of Vivitrol, vulnerability to relapse may be more gradual, and the instance of mild or equivocal reactions to the naloxone challenge more common. In this instance, a second challenge within 72 hours, will be attempted, and if tolerated, the next injection of Vivitrol can be given. Patients who fail two consecutive naloxone challenges are considered to have relapsed and are referred for inpatient detoxification or agonist maintenance, as deemed clinically appropriate and in accordance with the patient's wishes. **Patients who fail two negative naloxone challenges will be given a week supply of buprenorphine and will be provided with referrals.**

Missing a scheduled Vivitrol injection is the most important threat to the success of Vivitrol maintenance. In the event of a patient missing a scheduled injection, staff will immediately attempt to contact the patient to re-establish commitment to the naltrexone treatment and reschedule the injection within a 24-48 hour period. If the patient cannot attend the treatment center within a two-day time-frame, or cannot be located, the treatment team will use previously obtained locator information in an effort to locate the patient through emergency contacts and try to get them in for a visit.

Study Visits

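### The naloxone challenge before a delayed Vivitrol injection is stated in two conflicting ways: optional after two days of opioid use in one section, compulsory with no day count in another

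*Protocol*

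**What the plan says.** Three places in the Protocol deal with the challenge.

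- **Procedures for Missed Doses of Vivitrol.** The rule applies to a patient who misses the second or third injection and "takes an opioid during at least two of the seven days following the date of the scheduled injection". It continues: "relapse will be suspected (the participant reports recent opioid use, and/or has a positive UDS for opioids". Then "a naloxone challenge may be performed, if appropriate", with 0.8 mg naloxone IM. A negative challenge leads back to Vivitrol. A mild or equivocal reaction leads to a second challenge within 72 hours, and Vivitrol can follow if that is tolerated. The section asks staff to "reschedule the injection within a 24-48 hour period", and it notes that "there are blood levels and partial blockade beyond four weeks after the initial administration of Vivitrol".
- **Naltrexone induction procedure.** This paragraph presents its rule as the one noted in the missed-dose section. It applies "if relapse is suspected (the participant reports opioid use, and/or has a positive UDS for opioids". A second condition must hold as well, namely that "there is a risk that the participant has developed physical dependence", for which it gives a delayed injection and an apparently incomplete block as examples. The challenge is then to be given before the next injection, with no discretion expressed.
- **Side Effects of Extended-Release (XR), Injectable Naltrexone.** After a missed injection and a return to regular use, the physician is to evaluate the patient and carry out the challenge. The section warns that withdrawal precipitated by the injection may be quite severe, depending on time since the last injection and level of dependence.

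**The concern.** The missed-dose section is where staff would look after a missed injection, and the induction paragraph names it as the source of the rule. Yet the two differ on how much opioid use counts, on whether dependence risk is a condition, and on whether the challenge is optional.

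Two clinicians could therefore handle the same patient differently. Take a patient whose injection is a day late, who reports one day of use, and who is judged at risk of dependence. Under the induction paragraph the challenge is compulsory. Under the missed-dose section the day count is not met. At stake are the risk of precipitated withdrawal after a 380 mg depot injection and consistent handling before the second and third injections, receipt of which is the first item under Secondary Endpoint in the SAP.

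**Working it through.** The plan gives no figure to reproduce here; the main check is a comparison of texts.

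**1. The rules side by side**

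| | Missed-dose section | Induction paragraph | Side-effects section |
|---|---|---|---|
| Setting | Second or third injection missed | Next injection; delay is one example | Injection missed |
| Opioid use | Two or more of seven days; a parenthesis adds report and/or positive urine, uncounted | Report and/or positive urine, no count | Return to regular use |
| Dependence risk | Not named | Required | Not a separate condition |
| Force | May, if appropriate | Will, before next injection | Physician will perform it |

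**2. Can the texts be reconciled?** Suppose the induction paragraph silently imports the two-day count, because it says it follows the missed-dose section. The use triggers then agree, but *may* against *will* remains. Suppose instead that the phrase about appropriateness stands for the dependence-risk judgement. The count still differs, and the challenge is still not stated as required once risk is present. Neither reading removes the whole conflict.

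**3. Timing.** Let k be the number of days from the scheduled date to the return. Days of use since that date cannot exceed k.

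- k = 1 (24 hours): at most 1 day of use, and 1 < 2, so the count cannot be met even by a daily user.
- k = 2 (48 hours): it is met only by use on both days.
- The parenthesis on reported use or positive urine carries no count, so the missed-dose sentence is unclear on its own terms.

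**4. How far apart are the two use triggers?** They differ when there is exactly one day of use. With an assumed daily use probability q, independent between days (the documents give neither), P(exactly one day) = k × q × (1 − q)^(k−1).

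| q (assumed) | 0.3 | 0.5 | 0.7 | 0.8 | 1.0 |
|---|---|---|---|---|---|
| k = 1 | 0.30 | 0.50 | 0.70 | 0.80 | 1.00 |
| k = 2 | 0.42 | 0.50 | 0.42 | 0.32 | 0 |
| k = 7 | 0.247 | 0.055 | 0.004 | 0.000 | 0 |

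For example, k = 2 and q = 0.3 gives 2 × 0.3 × 0.7 = 0.42. These figures compare the use triggers only and leave out the dependence-risk condition.

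**5. Ceiling on extra workload.** The inputs are 30 completers and 45 enrolled (Protocol, Description of Subject Population) and the hypothesised 65% reaching a first injection (SAP, Hypothesis).

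- First injections: 0.65 × 30 = 19.5 to 0.65 × 45 = 29.25.
- Second and third injections due, with no dropout (an upper bound): 2 × 19.5 = 39.0 to 2 × 29.25 = 58.5.
- Missed, assuming 10% to 40%: 0.10 × 39.0 = 3.9 to 0.40 × 58.5 = 23.4.
- One-day users at a 48-hour return, at most: 0.50 × 23.4 = 11.7. If half are judged at dependence risk this is 5.9; if a quarter, 2.9.

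**The case against.** The best defence is that the missed-dose section has its own safeguard. It describes resuming Vivitrol after a negative challenge, or after a second one that is tolerated, and for a patient with suspected relapse it describes no other route back to injection. The optional wording may simply spare patients who are clearly moving to agonist treatment. The induction paragraph and the side-effects section state the challenge as required, and nothing in the missed-dose section forbids one below two days of use. A seven-day count also suits the patients, for whom that section separately provides, who cannot return within two days.

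Most of this stands. It limits the harm to staff working from the missed-dose section alone. It does not remove the contradiction: a section cited as the source of a compulsory rule should not state that rule as optional and with a different trigger.

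A reader might infer from the table of assumed use rates that up to half of late patients, or more at 24 hours, would be injected unsafely. The documents do not support that. The use rates are assumed, dependence risk is left out, and the patients in question have used on one day only, in a setting where the Protocol itself expects partial blockade to persist. One day of use in a short delay is not shown to carry the hazard.

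**Conclusion.** Wrong as written, as an internally contradictory safety rule, and minor. The finding rests on the current text of the sections compared and needs none of the assumed rates. The likely consequence is inconsistent handling if staff follow the missed-dose section by itself. No rate of unsafe injections can be derived, because the Protocol and SAP give no rates of missed injections, daily use or dependence risk.

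A reader might also suspect an effect on the main result. There is none: the primary endpoint is receipt of the first injection, and the missed-dose rule governs only the second and third.

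**What to change.** In Procedures for Missed Doses of Vivitrol, replace the opening sentence with wording such as:

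> If a scheduled second or third injection is missed and the participant reports opioid use, has an opioid-positive urine, or both, relapse is suspected. If physical dependence may have developed, naloxone 0.8 mg IM will be given as a challenge before any further Vivitrol. Risk may be judged from the delay or from effects suggesting incomplete blockade; it is taken as present in every case of opioid use on two or more days since the scheduled date. A participant who will not resume Vivitrol needs no challenge.

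This keeps the one countable criterion as a sufficient condition and leaves judgement for lesser use. The induction paragraph can stay.

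In the side-effects section, leave the obligation to challenge after resumed regular use unconditional. Add only a cross-reference saying that a mild or equivocal reaction is handled by the second challenge within 72 hours. Otherwise that section's removal of anyone with a positive challenge conflicts with the missed-dose section.

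The cost is one short amendment. Urine and self-report are already collected at every visit. Compared with the missed-dose section read alone, and taking its optional challenge as done whenever the count is met, extra challenges at 48-hour returns are at most about 12 under the assumptions above. About 3 to 6 follow if a quarter to a half of the one-day users are judged at risk. The outer limit, every missed injection leading to an extra challenge, is about 23. Compared with the induction paragraph there should be few or none, since delay already counts there as an example of risk. Each challenge takes about 45 minutes by the Naloxone Challenge Test section, or an hour by the missed-dose section ("withdrawal symptoms are assessed over the next hour"), and may cause withdrawal discomfort.

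### After a missed second or third Vivitrol injection with suspected relapse, the missed-dose section makes the naloxone challenge optional and sets a narrower trigger than the section that requires it

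*Protocol*

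**What the plan says.** Three places in the Protocol deal with a patient who is late for a Vivitrol injection and may have gone back to opioids.

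- **Procedures for Missed Doses of Vivitrol.** This covers a missed second or third injection. Relapse is suspected if the patient "takes an opioid during at least two of the seven days following the date of the scheduled injection", followed by a parenthesis naming recent self-reported use and/or a positive urine screen. Then "a naloxone challenge may be performed, if appropriate, using 0.8mg naloxone IM". If the test is negative, Vivitrol resumes. For a mild or equivocal reaction, "a second challenge within 72 hours, will be attempted, and if tolerated, the next injection of Vivitrol can be given". Two consecutive failures count as relapse. The same section tells staff to contact the patient at once and "reschedule the injection within a 24-48 hour period".
- **Naltrexone induction procedure.** The paragraph on dosing days points to the section above: "As noted in the section for Procedures for Missed Doses of Vivitrol, if relapse is suspected (the participant reports opioid use" or has a positive urine screen, and there is a risk of physical dependence. Its examples of that risk are "delay in receiving scheduled injection or subjective effects suggesting that the block is incomplete". In that case "a naloxone challenge will be administered before the participant receives their next injection".
- **Side Effects of Extended-Release (XR), Injectable Naltrexone** (under Risks). When an injection has been missed and regular opiate use has resumed, the physician evaluates the patient and performs a challenge. A positive result, meaning that withdrawal is precipitated, leads to removal from the study.

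**The concern.** The challenge is the safeguard against giving a month-long antagonist to someone who has become physically dependent again. The Protocol's own risk section warns that the resulting withdrawal can be quite severe. Staff handling a missed injection will open the missed-dose section. That section has the weakest wording of the three, and its day-count condition leaves out some patients whom the induction section would test. The firm rule sits at the end of a paragraph about oral naltrexone dosing, where someone managing a missed maintenance dose is less likely to look.

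What is at stake is mainly the safety of individual patients. There is also a secondary analytic interest: the SAP's first secondary outcome is the proportion retained to receive the second and third injections, and these rules decide who may be injected late.

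**Working it through.** The plan states no figure on this point, so there is none to reproduce. The check is a comparison of the texts plus a count of elapsed days.

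**1. Do the sections cover the same patient?** The induction section's rule has two conditions: suspected relapse and a risk of physical dependence. A delayed injection is its own example of the second. A patient who has missed a scheduled injection and is suspected of relapse therefore meets both conditions, and this is the patient the missed-dose section addresses. The induction section also cites that section by name.

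**2. Is the challenge required, and on what trigger?**

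| Section | Status of the challenge | Trigger |
|---|---|---|
| Missed doses | Optional | Missed second or third injection, and use on 2 or more of the next 7 days; parenthesis adds recent self-report and/or positive urine screen |
| Naltrexone induction | Required before the next injection | Self-report and/or positive urine screen, plus a dependence risk such as a late injection; no minimum number of days |
| Side effects of injectable naltrexone | Physician performs it | Missed injection and resumed regular use (number of days not defined) |

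For the same patient, one section permits the test while the section citing it requires it. The risk section agrees with the requirement.

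**3. Does the day count fit the rebooking window?** Take the 24 to 48 hours as running from the missed date.

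- Seen at 24 hours: 1 day has elapsed and 2 days of use are needed. Since 1 < 2, the condition cannot be met.
- Seen at 48 hours: 2 days have elapsed, so use on 2 of 2 days is needed.
- One day of use, whenever the patient is seen: 1 < 2, so the condition is not met.

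A late patient with one day of use, by self-report or urine screen, must be tested under the induction section but does not meet the missed-dose section's count. The third line does not depend on when the clock starts. The count also looks only at days after the scheduled date, while the induction section has no such limit.

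**4. How are reactions handled?** The missed-dose section sends a mild or equivocal reaction to a repeat test. The risk section removes a patient whose test is positive and says nothing about equivocal results. The two fit together if equivocal is read as not yet positive, but neither section refers to the other on this. The gap is worth closing because the missed-dose section expects, in this setting, "the instance of mild or equivocal reactions to the naloxone challenge more common".

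**The case against.** The strongest reply is that the protection is already there when the Protocol is read as a whole. Nothing authorises injecting a suspected-relapse patient at risk of dependence without a test. Straight after the optional wording, the missed-dose section treats the challenge as a gate: Vivitrol resumes if it is negative and, after an equivocal result, only if the repeat is tolerated. The qualifier about appropriateness could simply spare an obviously dependent patient a pointless test before referral. This argument stands as evidence of intent. A reader might infer that the Protocol allows patients to be injected untested, and the documents do not support going that far. The argument still does not remove the permissive wording or the narrower trigger.

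A second reply is that the triggers are closer than a bare reading suggests. The missed-dose section's parenthesis nearly repeats the induction section's definition of suspected relapse, and the risk section's phrase about regular use describes when injection would precipitate withdrawal more than it sets an operating rule. Both points are fair, so this is not a case of three competing triggers. But the parenthesis follows the day count and does not replace it, so the one-day patient is still left out.

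Third, the rebooking window might run from contact with the patient, the seven-day span suits patients who are hard to locate, and persisting partial blockade is a plausible reason to ask for more than one day of use. That weakens the 24- and 48-hour lines above. It leaves the one-day gap as it is.

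A reader might also infer that the mild-reaction rules contradict each other. They can largely be read together, and leaving the call to a supervising physician is a legitimate choice.

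**Conclusion.** The inconsistency holds. The section that staff will use for a missed injection makes the challenge optional and conditions it on a day count. The section that cites it makes the challenge mandatory on a broader trigger, and the risk section also has it performed. The text around the optional wording suggests that a mandatory test was intended, so the correction restores that intent and sets no new policy.

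This is a minor safety correction. The primary endpoint, receipt of the first injection, is settled before any of these rules apply. Only patients who received a first injection, missed a later one and used opioids can be affected. The documents give no rate for that group, so no effect on the second- and third-injection outcome is claimed. A reader might infer a material bias in that outcome, but nothing in the documents supports one.

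The conclusion assumes that the missed-dose day count is meant as a condition for suspecting relapse, as its sentence order indicates, and that a missed injection counts as a delayed one under the induction section.

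**What to change.** In *Procedures for Missed Doses of Vivitrol*:

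- Replace the optional wording with a statement that the challenge *will be performed before any further Vivitrol injection*, keeping the 0.8 mg IM dose and the hour of observation.
- Replace the two-of-seven-days condition with the induction section's trigger: self-reported opioid use and/or a positive urine screen, plus a delayed injection or signs that the block is incomplete.

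In *Side Effects of Extended-Release (XR), Injectable Naltrexone*, add a cross-reference to the missed-dose section. A mild or equivocal reaction then goes to the repeat challenge within 72 hours, and a clearly positive challenge or two consecutive failures leads to removal.

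The cost is one clarifying amendment to two sections and an occasional extra challenge of about one hour for a patient who would otherwise not have been tested. The SAP needs no change.

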Participants will be seen in the center twice weekly during the buprenorphine stabilization phase and daily on weekdays during the induction phase (Days 1-5). Once XR-NTX has been administered, participants will continue to be seen at the center twice weekly for 12 weeks. At each visit the patient will meet with the research assistant to complete research ratings. Research nurse collects safety measures and inquires about side effects. Side effects of study medications are reviewed weekly during the visit with a research psychiatrist, or more frequently if clinically indicated, and study psychiatrist will adjust medication dose if necessary.

At each visit the patient meets with the research assistant to complete research ratings, including self-report of withdrawal, mood, and drug use. The patient provides a urine sample under observation by a staff member at each visit. The sample is tested immediately for opiates with the iScreen system (Instant Technologies, Inc.). Vital signs are also taken. All data are then brought to the therapist and therapy session is held.

Participants may come to the center to be seen as frequently as needed. In particular, any participant who is experiencing protracted opioid withdrawal will be offered clinical contact on a frequent, even daily, basis. For clinical matters arising in the evenings or on weekends, participants will have access to the 24-hour emergency telephone service, staffed by physicians familiar with this protocol who can address patients' concerns.

Behavioral Therapy

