All participants who remain active in treatment will have an End-of-Study visit, within a week of the final study day (28 days after second XR-NTX injection), during which final ratings measures, and toxicology will be obtained. Participants will receive a third injection of XR-NTX at the end of study. At the conclusion of the protocol, the participants will be offered supportive therapy for at least one additional month or until an appropriate referral for on-going treatment is made. If the patient is interested to continue on XR-NTX, we will try to work with the patient's insurance to provide coverage to continue XR-NTX. Most insurance plans cover Vivitrol, and we have developed a network of providers who we have referred patients to. If the patient is unable to find a provider to administer injection but we were able to secure the medication through patient's insurance and the patient is at risk to become unblocked we will administer the injection.

Participants who had no response to naltrexone treatment, such as those who continued using opioids while on naltrexone as well as those who stopped taking naltrexone (missed scheduled injections) and/or resumed opioids after missing naltrexone, are considered to be at very high risk of a full relapse and overdose.

These individuals will be immediately directed toward either inpatient detoxification followed by a residential treatment, or toward agonist maintenance with either buprenorphine/naloxone or methadone. Methadone maintenance treatment is widely available in the community; however, access to buprenorphine treatment is more restricted.

In order to minimize the risk of relapse due to the lack of access to the medication and the gap between treatment providers we would like to offer 2-week supply buprenorphine/naloxone 8mg to participants who are in the process of being referred out to either inpatient treatment or an agonist maintenance program. We will continue to provide additional support including frequent, daily if needed visits at our center for a maximum of 2 weeks.

Clinical Treatment Alternatives

Clinical treatment alternatives

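### The protocol's end-of-study text closes the trial at about day 56, the day of the third injection, while its visit schedule runs to day 84

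*Protocol*

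**What the plan says.** Protocol, Study Visits: "Once XR-NTX has been administered, participants will continue to be seen at the center twice weekly for 12 weeks". The same section has the research assistant complete ratings and the nurse collect safety measures, and adds "The patient provides a urine sample under observation by a staff member at each visit". These are research visits, not aftercare.

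Protocol, Vivitrol Injections: "Participants will be offered a second injection 4 weeks post administration of the first injection, and a 3rd injection 4 weeks later".

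Protocol, Treatment to be provided at the end of the study: for participants still in active treatment, the timing of the closing visit is given as "within a week of the final study day (28 days after second XR-NTX injection"). What is collected at that visit is described separately: "during which final ratings measures, and toxicology will be obtained". On the last dose, the section says "Participants will receive a third injection of XR-NTX at the end of study". After the protocol concludes, participants are "offered supportive therapy for at least one additional month", or until they are referred.

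Two other assessments depend on the end date. Blood chemistry is scheduled at baseline and end of study (Blood and other Biological Samples), and the physical exam at the screening and End-of-Study visits (Assessment Instruments).

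The SAP lists adverse events, longitudinal withdrawal, sleep, mood and anxiety measures, and an abstinence summary as secondary outcomes. It gives no time window for any of them.

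**The concern.** Ratings and toxicology cannot be final at about day 56 and also continue twice weekly to day 84. The two sections disagree on when research follow-up stops, and the SAP does not settle it.

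What is at stake is the four weeks after the third injection. Receipt of that injection is itself a secondary outcome, so the dose is a trial exposure, and safety is a stated secondary objective. If the end-of-study text is followed, adverse events, opioid use, mood and withdrawal in those weeks largely fall outside the trial. The one scheduled post-baseline chemistry and physical exam would be done at about the time of the dose rather than after it. In a single-arm study with mostly descriptive outcomes, the observation window largely determines what is reported.

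**Working it through.** Count from the first injection as day 0, with injections on time.

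**Dates**
- Second injection: 4 × 7 = day 28. Third: 28 + 28 = day 56 (Vivitrol Injections).
- Final study day in the end-of-study section: 28 + 28 = day 56, the day of the third injection. Reading the one-week allowance as two-sided, the End-of-Study visit falls on days 49 to 63.
- Visit schedule: 12 × 7 = day 84 (Study Visits).
- Gap: 84 − 56 = 28 days. Against the latest End-of-Study visit it is still 84 − 63 = 21 days, so the allowance does not close it.

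**Visits and follow-up**
- Twice-weekly visits after the first injection: 8 × 2 = 16 against 12 × 2 = 24. Eight of 24 are in conflict.
- Research follow-up after the third injection: at most 63 − 56 = 7 days, against 84 − 56 = 28 days.
- Illustration, taking abstinence as the share of scheduled visits (the SAP does not define the measure this way): a participant abstinent at the first 16 visits and not at the next 8 scores 16/16 = 100% on one window and 16/24 = 67% on the other.

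**Can the two sections be reconciled?**
- The extra month of supportive therapy does not account for the gap. It follows the conclusion of the protocol and no ratings or urine are attached to it, while Study Visits requires both.
- Twelve weeks as the whole study (3 weeks of buprenorphine + 1 of induction + 8 after injection) fits numerically, but Study Visits counts from administration of XR-NTX.

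**Which end date does the payment cap favour?**
- Paid visits: $1,720 / $40 = 43 (Compensation and/or Reimbursement).
- Other visits, excluding screening (assumed): consent 1, buprenorphine phase 6 to 7, washout 2, naltrexone induction 3 to 5, End-of-Study 1. Total 13 to 16.
- 12-week schedule: 43 − 24 = 19, leaving 19 − 16 = 3 to 19 − 13 = 6 for screening.
- 8-week schedule: 43 − 16 = 27, leaving 27 − 16 = 11 to 27 − 13 = 14 for screening.

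The number of screening visits is not stated, but 3 to 6 is far more plausible than 11 to 14.

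**The case against.** The strongest reply is that Study Visits is the operative schedule and is explicit, whereas the conflicting sentences sit in a form field mainly about aftercare. Assessment Instruments also schedules urine, withdrawal and craving measures through the post-induction phase with no earlier stop, and the payment cap points the same way. Staff would probably follow the 12 weeks, and nothing would be lost except a correctly timed chemistry and exam. Most of this stands. It makes the end-of-study text the likely error and keeps the point minor. It does not remove the conflict, because that section is the only one that defines a final study day and says when final ratings are taken.

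A reader might infer that the two end dates are evenly balanced, or that the trial will lose four weeks of data. The documents do not support either: if Study Visits is followed, ratings, safety measures and urine are collected to day 84.

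Two smaller objections also stand. The early half of the visit window is doubtful, since a day-49 visit would precede an injection said to be given at the end of study; only the later limit, day 63, matters here. And the End-of-Study visit is limited to participants still in active treatment, so a repair should not quietly extend it to everyone who was inducted.

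**Conclusion.** The end-of-study section is inconsistent with the visit schedule by 28 days and 8 of 24 visits, and it is probably the section in error. The dates assume on-time injections; the judgement about which section is wrong rests partly on the assumed 13 to 16 other visits. If the end-of-study section is followed, the third injection has at most about a week of research follow-up, and the only scheduled post-baseline chemistry and exam come at about that dose.

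The point is minor. It would be wrong to infer any effect on the main result: the primary endpoint is receipt of the first injection, receipt of the second and third is settled by day 56 when on time, and the sample size of 30 does not depend on follow-up length. How many participants would still be attending after a third injection is not given, so the number affected cannot be stated.

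**What to change.** In the protocol section on treatment at the end of the study:
- set the final study day at 12 weeks (day 84) after the first injection, which equals 28 days after an on-time third injection;
- state that the third injection is given at week 8, not at the end of study;
- hold the End-of-Study visit, with blood chemistry and physical exam, at day 84 for participants still in active treatment, the group to which that section already limits it.

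In the SAP, add one line using the same 12-week window after the first injection for adverse events, longitudinal measures and abstinence.

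The cost is small, because Study Visits already schedules the visits to day 84. There are two downsides. End-of-study chemistry and exam come about 4 weeks later. A late injection also shortens follow-up after the third dose: the missed-dose procedure aims to "reschedule the injection within a 24-48 hour period", and a third injection delayed by that much leaves 28 − 1 = 27 or 28 − 2 = 26 days. A late second injection that pushes back the third has the same effect. Tying the End-of-Study visit to 28 days after the third injection would avoid this for those who receive it, but gives no end date for a participant still in treatment who does not. The sponsor should choose one rule and state it.
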